Eosinophilia associated with clinical symptoms in asthma patients is an important potential risk, based on cases of eosinophilic granulomatosis with polyangiitis and eosinophilic pneumonia reported in asthma clinical trials (as well as in adult patients with co-morbid asthma in the CRSwNP development program). These events may usually, but not always, be associated with the reduction of oral corticosteroid therapy. A causal association between dupilumab and these conditions has not been established In the AD clinical studies, Conjunctivitis, Conjunctivitis Allergic, Conjunctivitis Bacterial, Blepharitis, Dry Eye, Eye Pruritus, Herpes Simplex (primarily mucocutaneous in nature), Eosinophilia and Oral Herpes were identified ADRs. The eye and herpes related ADRs appear to be predominantly AD indication specific. Conjunctivitis is also considered an ADR for the CRSwNP indication, although it occurred at a lower incidence in these studies than in AD studies. Most events were mild in intensity, transient in nature, and did not necessitate treatment discontinuation. Conjunctivitis and keratitis related events in AD patients are an important identified risk for dupilumab. In the completed AD studies in children 6 to 17 years of age, the safety profile was consistent with that reported in adults and there were no new safety concerns identified. In a study in participants aged 6 to 11 years with asthma, Enterobiasis and Eosinophilia were identified as additional ADRs. Angioedema, Arthralgia, Keratitis, Ulcerative Keratitis, and Facial Rash have been identified as ADRs in the post marketing setting. The program has a data monitoring committee (DMC), which will review the benefit/risk on a regular basis. A complete efficacy and safety profile of dupilumab, with respect to the overall development program, is provided in the Investigator's Brochure.

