#### 7.2.1. Inclusion Criteria

A patient must meet the following criteria to be eligible for inclusion in the study:

- 1. Males and females  $\geq 12$  years of age at screening
- 2. Diagnosis of ABPA defined by the following criteria at screening:

Obligatory criteria at screening (must meet all 3 of the following criteria):

REGENERON CONFIDENTIAL Page 40 of 99

- a. Physician diagnosis of asthma for at least 12 months based on the Global Initiative for Asthma (GINA) 2019 guidelines
- b. Evidence of sensitization to *A fumigatus* by skin testing (at screening or documented historical positive skin test in the previous 12 months), or elevated *A fumigatus*-specific IgE in serum (≥0.35 kU/L) at screening
- c. Elevated serum total IgE >1000 IU/mL. If all 3 supportive criteria for ABPA (below) are met, IgE  $\leq$ 1000 IU/mL is acceptable. If the patient is receiving OCS at screening, a documented historical IgE > 1000 IU/mL within the previous 12 months is acceptable

And 2 or more of the following supportive criteria:

- a. For patients on OCS, blood eosinophil count >500 cells/µL at screening or a documented historical blood eosinophil count >500 cells/µL within 12 months of screening. For patients not on OCS, blood eosinophil count >500 cells/µL at screening or blood eosinophil ≥300 to ≤500 cells/µL at screening with a documented historical blood eosinophil count >500 cells/µL within 12 months of screening.
- b. The presence of serum precipitating or IgG antibodies to *A fumigatus* at screening or a documented historical positive result for one of these tests within 12 months prior to screening
- c. Documented radiological findings consistent with ABPA (such as fleeting pulmonary parenchymal opacities, mucoid impaction, high-attenuation mucus, centrilobular nodular opacities, atelectasis, bronchiectasis, etc) by historical chest x-ray or chest computed tomography (CT) or magnetic resonance imaging (MRI) within the previous 18 months or at screening

NOTE: A total of 2 attempts may be made during the screening period until the baseline visit to meet the qualifying criteria for blood eosinophils, total serum IgE, Aspergillus-specific IgE, Aspergillus-specific IgG, Aspergillus precipitins, and/or skin prick test

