#### Abnormal Laboratory Values and Laboratory Adverse Events

All laboratory values must be reviewed by the investigator or authorized designee.

Significantly abnormal test results that occur after start of treatment must be repeated to confirm the nature and degree of the abnormality. When necessary, appropriate ancillary investigations should be initiated. If the abnormality fails to resolve or cannot be explained by events or conditions unrelated to the study medication or its administration, the medical/study director must be consulted.

The clinical significance of an abnormal test value, within the context of the disease under study, must be determined by the investigator.

Criteria for reporting laboratory values as an AE are provided in Section 10.1.1.

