## **10. SAFETY EVALUATION AND REPORTING**

#### **10.1.** Recording and Reporting Adverse Events

#### 10.1.1. General Guidelines

The investigator must promptly record all clinical events occurring during the study data collection period (see Section 11.4.5.1). Medical conditions that existed or were diagnosed prior to the signing of the ICF will be recorded as part of medical history. Abnormal laboratory values and vital signs observed at the time of informed consent should also be recorded as medical history. Any subsequent worsening (ie, any clinically significant change in frequency and/or intensity) of a pre-existing condition that is temporally associated with the use of the study drug should also be recorded as an AE.

At each visit, the investigator will determine whether any AEs have occurred by evaluating the patient. Adverse events may be directly observed, reported spontaneously by the patient or by questioning the patient at each study visit. Patients should be questioned in a general way, without asking about the occurrence of any specific symptoms. The investigator must assess all AEs to determine seriousness, severity, and causality, in accordance with the definitions in Section 10.2. The investigator's assessment must be clearly documented in the site's source documentation with the investigator's signature. The investigator should follow up on SAEs (and adverse events of special interest [AESIs]) until they have resolved or are considered clinically stable; AEs should be followed until they are resolved or last study visit, whichever comes first.

Always report the diagnosis as the AE or SAE term. When a diagnosis is unavailable, report the primary sign or symptom as the AE or SAE term with additional details included in the narrative until the diagnosis becomes available. If the signs and symptoms are distinct and do not suggest a common diagnosis, report them as individual entries of AE or SAE.

Laboratory results, vital signs, and other diagnostic results or findings should be appraised by the investigator to determine their clinical significance. Isolated abnormal laboratory results, vital sign findings, or other diagnostic findings (ie, not part of a reported diagnosis) should be reported as AEs if they are symptomatic, lead to study drug discontinuation or dose reduction, require corrective treatment, or constitute an AE in the investigator's clinical judgment.

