10.1.1. Adverse Events of Special Interest

Adverse events of special interest for this study are as follows:

- Anaphylactic reactions
- Systemic hypersensitivity reactions
- Helminthic infections
- Any severe type of conjunctivitis or blepharitis
- Keratitis
- Clinically symptomatic eosinophilia (or eosinophilia associated with clinical symptoms)

Summaries of treatment-emergent AESIs by AESI category, primary SOC, and PT using the search criteria specified in [Table 1](#) will be presented.

Table 1: AESI Categories and Corresponding Search Criteria

AESI Category	Search Criteria
Anaphylactic reactions	Narrow SMQ for “Anaphylactic reaction”
Systemic hypersensitivity reactions (excluding events already included under anaphylactic reactions)	Narrow SMQ for “Hypersensitivity” minus narrow SMQ for “Anaphylactic reaction”, followed by blinded adjudication by the Sponsor clinical team
Helminthic infections	HLT of “Cestode infections” or “Helminthic infections NEC” or “Nematode infections” or “Trematode infections”
Any severe type of conjunctivitis or blepharitis	(Broad CMQ for “Conjunctivitis” or any PT containing “blepharitis” and with severity recorded as “Severe”
Keratitis	Narrow SMQ for “Corneal disorders”
Clinically symptomatic eosinophilia (or eosinophilia associated with clinical symptoms)	HLT of “Eosinophilic disorders” or PT of “Eosinophil count increased”, followed by blinded adjudication by the Sponsor clinical team

Note: PTs included in this table are based on MedDRA® version 26.1. If a more recent version of MedDRA® is available and is used for reporting purposes, the PTs used in the programming logic for the search criteria will be updated accordingly.

AESI=adverse event of special interest; CMQ=custom MedDRA® query; HLT=High Level Term; MedDRA®=Medical Dictionary for Regulatory Activities; NEC=not elsewhere classified; PT=preferred term; SMQ=standardized MedDRA® query.

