Significantly abnormal test results that occur after the start of study treatment must be repeated to confirm the nature and degree of the abnormality. When necessary, appropriate ancillary investigations should be initiated. If the abnormality fails to resolve or cannot be explained by events or conditions unrelated to the study drug or its administration, the medical/study director must be consulted.

The clinical significance of an abnormal test value, within the context of the disease under study, must be determined by the investigator.

Criteria for reporting laboratory values as an AE are provided in Section 10.1.1 of the protocol.

Clinical laboratory analytes will be converted to standard international (SI) units and grouped by function in summary tables. Clinical laboratory values and change from baseline in clinical laboratory values at all scheduled post-baseline assessment time points will be summarized via descriptive statistics by treatment group.

Patient laboratory parameter measurements will be evaluated by PCSV criteria, specifically identifying patients with at least 1 post-baseline measurement that meets the PCSV criteria (see Section 14.3). Patients meeting the PCSV criteria will be summarized by patient count (and percentage) for a post-baseline PCSV measurement by treatment group. When the PCSV definition involves a change from baseline value, patients must have a baseline value to be included in the summaries. All measurements collected during the study, including values from unscheduled visits, will be used in the PCSV analyses.

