Glucose	Hypoglycaemia: (>3.9 mmol/L or \geq LLN) at baseline and (≤3.9 mmol/L and $<$ LLN) post-baseline Hyperglycaemia: <7 mmol/L at baseline (fasted) and ≥7 mmol/L post-baseline (fasted); <11.1 mmol/L at baseline (unfasted) and ≥11.1 mmol/L post-baseline (unfasted)	ADA May 2005. ADA Jan 2008.
Potassium	≥3 mmol/L at baseline and <3 mmol/L post-baseline <5.5 mmol/L at baseline and ≥5.5 mmol/L post-baseline	
Sodium	>129 mmol/L at baseline and ≤129 mmol/L post-baseline <160 mmol/L at baseline and ≥160 mmol/L post-baseline	
Total Bilirubin	$\leq1.5 \times$ ULN* at baseline and >1.5 and $\leq2 \times$ ULN post-baseline $\leq2.0 \times$ ULN at baseline and $>2 \times$ ULN post-baseline	Must be expressed in ULN, not in μ mol/L or mg/L. Concept paper on DILI – FDA draft Guidance Oct 2007. * At least one level is required, multiple levels are optional for phase 2/3 studies.
Total Cholesterol	<7.74 mmol/L at baseline and ≥7.74 mmol/L post-baseline	Threshold for therapeutic intervention.
Triglycerides	<4.6 mmol/L at baseline and ≥4.6 mmol/L post-baseline	Threshold for therapeutic intervention.
Uric Acid	≥0.12 mmol/L at baseline and <0.12 mmol/L post-baseline ≤0.408 mmol/L at baseline and >0.408 mmol/L post-baseline	
ECG		
HR	≤50 beats per minute post-baseline and decrease from baseline by ≥20 beats per minute ≥120 beats per minute post-baseline and increase from baseline by ≥20 beats per minute	Ref.: CPMP 1997 guideline.
PR	≥220 ms post-baseline and increase from baseline by ≥20 ms	Ref.: CPMP 1997 guideline.
QRS	<120 ms at baseline and ≥120 ms post-baseline	Ref.: CPMP 1997 guideline.
QTcB/QTcF	Borderline: <431 ms at baseline and 431-450 ms post-baseline for Male; <451 ms at baseline and 451-470 ms post-baseline for Female Prolonged: ≤450 ms at baseline and >450 to <500 ms post-baseline for Male; ≤470 ms at baseline and >470 to <500 ms post-baseline for Female <500 ms at baseline and ≥500 ms post-baseline Increase from baseline	Ref.: CPMP 1997 guideline. 5 independent criteria

[figure not shown]
Parameter	PCSV	Comments
	Borderline: Increase from baseline by 30-60 ms Prolonged: Increase from baseline by >60 ms	
Hematology		
Basophils	≤0.1 Giga/L at baseline and >0.1 Giga/L post-baseline	
Eosinophils	(≤0.5 Giga/L or ≤ULN) at baseline and (>0.5 Giga/L and >ULN) post-baseline	

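### The only legible eosinophil PCSV row in SAP 14.3 cannot flag a rise in a patient who starts above both 0.5 Giga/L and ULN, so no legible output counts such rises by arm.

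*SAP*

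**What the plan says.** **The row.** Under Hematology, SAP 14.3 has one legible eosinophil criterion: "≤0.5 Giga/L or ≤ULN) at baseline and (>0.5 Giga/L and >ULN) post-baseline". SAP 10.2 counts patients by treatment group who meet a criterion at least once after baseline, and lets unscheduled values count. SAP 1.4 keeps a single set of PCSV tables, on the ground that the criteria are mostly changes from baseline.

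**The population.** Protocol 7.2.1 requires the obligatory ABPA criteria "And 2 or more of the following supportive criteria". An eosinophil count above 500 cells/µL is one of three supportive criteria, and it can be met in part or in full from history.

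**The risk.** Protocol 3.3.1 states: "Eosinophilia associated with clinical symptoms in asthma patients is an important potential risk". It adds that the events "may usually, but not always, be associated with the reduction of oral corticosteroid therapy". Protocol 8.2 and Appendix A schedule an OCS taper for patients who are on OCS at baseline.

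**Other routes to detection.**
- Protocol 9.2.3.4: "All laboratory values must be reviewed by the investigator or authorized designee".
- Protocol 10.1.1: isolated abnormal results "should be reported as AEs if they are symptomatic, lead to study drug discontinuation or dose reduction, require corrective treatment", or if the investigator judges them to be AEs.
- SAP 10.1.1 lists as an AESI "Clinically symptomatic eosinophilia (or eosinophilia associated with clinical symptoms"), found by a coded-term search and blinded adjudication, with no baseline condition.
- SAP 10.2: "change from baseline in clinical laboratory values at all scheduled post-baseline assessment time points will be summarized via descriptive statistics by treatment group". SAP 4 defines those statistics to include the quartiles and the maximum.
- SAP 11.4 sends extra laboratory assessments to listings.

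**The concern.** A threshold-crossing rule works when most patients start below the threshold. Here the threshold of 0.5 Giga/L is the same number as the 500 cells/µL entry criterion, so some patients may well start above it. For them the row is switched off, while the protocol names eosinophilia with symptoms as an important potential risk.

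The stake is modest. The PCSV table is where the SAP turns laboratory values, including all unscheduled ones, into a count of patients per arm. If the eosinophil row is off for patients who start high, a difference between arms in laboratory rises among them, where nobody reported an AE, would have no count. A reader could also take a low count in that row as evidence of few rises, when part of it reflects patients who could not be flagged.

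**Working it through.** There is no planned figure to reproduce; the check is of the rule's logic.

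**Inputs.** The rule is from SAP 14.3. The ULN is not in the documents, so 0.4, 0.5 and 0.7 Giga/L are assumed for the examples and 0.35 to 0.70 for the grid. About 30 patients per arm is from Protocol 7.1.

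**Step 1: reduce the rule.** Baseline ≤0.5 or ≤ULN means baseline ≤ max(0.5, ULN). Post-baseline >0.5 and >ULN means post-baseline > max(0.5, ULN). The row is therefore

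baseline ≤ max(0.5, ULN) < post-baseline.

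It is off above 0.5 at an assumed ULN of 0.4 or 0.5, and above 0.7 at an assumed ULN of 0.7. A baseline above both limits is the exact negation of the first condition.

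**Step 2: confirm on a grid.** Values from 0 to 10 Giga/L in steps of 0.05, for ULN 0.35, 0.40, 0.45, 0.50, 0.60 and 0.70. Among pairs with baseline above both limits and a higher post-baseline value (17,205 to 17,955 per ULN), 0 were flagged.

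**Step 3: examples.** The last column applies an illustrative row: ≥100% increase from baseline, with post-baseline >0.5 Giga/L and >ULN.

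| Baseline → post (Giga/L) | Change | Existing row, ULN 0.4 or 0.5 | Existing row, ULN 0.7 | Illustrative row, ULN 0.5 |
|---|---|---|---|---|
| 0.4 → 0.9 | 0.5/0.4 = +125% | yes | yes | yes |
| 0.6 → 8.0 | 7.4/0.6 = +1233% | no | yes | yes |
| 0.8 → 1.5 | 0.7/0.8 = +87.5% | no | no | no |
| 0.8 → 8.0 | 7.2/0.8 = +900% | no | no | yes |
| 2.0 → 8.0 | 6.0/2.0 = +300% | no | no | yes |
| 1.2 → 1.2 | 0% | no | no | no |

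The 0.4 → 0.9 patient meets both rows. Unless the new row is split by baseline status, it would mix patients already counted with those now missed. A single higher crossing threshold would not serve instead: at 1.5 Giga/L it catches 0.8 → 8.0 but not 2.0 → 8.0.

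**Step 4: how many patients.** The documents give no baseline counts. If 20%, 40%, 60% or 80% of an arm started above both limits (assumed), then 30 × share = 6, 12, 18 or 24 patients per arm could not be flagged.

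**Step 5: look for the count elsewhere.**
- By-visit summaries describe the whole arm at one visit. They do not count patients across visits or separate those who started high.
- Scheduled hematology (Protocol Table 1) is at weeks 0, 4, 8, 12, 24, 36 and 44, EOT and EOS. Weeks 12 to 24, weeks 24 to 36, and EOT to EOS are each 12 weeks apart. Under SAP 11.4 an unscheduled value enters a by-visit summary only when it falls in the window of a scheduled visit with no value; otherwise it is listed.
- AE and AESI tables count reported events only.
- Laboratory shift tables are optional in Protocol 11.4.5.2 and are based on normal or abnormal at baseline, so abnormal to abnormal shows no shift. The SAP legibly plans shift tables only for ECG status.
- The WBC row (crossing 16.0 Giga/L) might catch an extreme rise, but it is not specific to eosinophils.

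**Separate small check.** The female low-hematocrit row is printed as ≥0.32 v/v at baseline and ≤0.32 v/v after. An unchanged 0.32 satisfies both. The male row uses >0.37 at baseline and does not have this property.

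**The case against.** The strongest reply is that little is lost. Every laboratory value is reviewed, and anything symptomatic or acted on becomes an AE. The AESI has no baseline condition, and it is the symptomatic form that the protocol calls a risk. With about 30 per arm, by-visit quartiles and maxima would reveal a sizeable shift or a striking outlier, and extra values reach the listings. Threshold crossing is the table's usual form. Protocol 3.3.1 also says that no causal link to dupilumab has been shown, and the OCS taper concerns only patients on OCS, some of whom qualify on historical counts and may start low enough for the row to work.

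All of that stands, and it limits the weight of the point. It does not supply the count. Quartiles bound the share of an arm that rose at one visit; they do not say how many patients rose at any time from a high baseline. Listings are not counts, and SAP 1.4 restricts them to those the study report requires.

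Baseline eosinophils are also summarized as a continuous variable with quartiles (SAP 6.2 and SAP 4), so a reader could bracket the share of patients above the limit, though not state it exactly.

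A reader might infer more: that eosinophilia goes undetected in these patients, or that the entry criteria put most of the trial above the limit. The documents support neither. Reported cases are captured, and the eosinophil criterion is one of three, of which two are needed.

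**Conclusion.** The point holds as a low-cost refinement of one safety table. That the row cannot flag a patient who starts above both limits is certain from its wording, whatever the ULN. That no other output counts these rises by arm holds for the legible text only; redacted biomarker and exploratory entries might contain an eosinophil analysis and cannot be checked.

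The number of patients affected is unknown, and the 6 to 24 per arm shown above is arithmetic on assumed shares. The primary FEV1 analysis is unaffected, and nothing here suggests a missed safety signal. The hematocrit remark is minor and depends on the sign being as printed.

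**What to change.** Before unblinding:

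1. Keep the existing eosinophil row. Beside it, show the number per arm whose baseline allows it to be met (≤0.5 Giga/L or ≤ULN).
2. Add to SAP 14.3 a rise-from-baseline eosinophil row, in the style already used for creatinine. An example is a ≥100% increase from baseline with a post-baseline value >0.5 Giga/L and >ULN. The sponsor sets the cut-off, knowing that 100% leaves out 0.8 → 1.5. Report the row separately for patients with baseline above both 0.5 Giga/L and ULN and for all others. In each group use patients with a non-zero baseline and at least one post-baseline value, since a zero baseline gives no percentage; the existing row still covers those patients.
3. If the sign is as printed, change the female low-hematocrit baseline condition from ≥0.32 v/v to >0.32 v/v.

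The SAP already has the pattern: creatinine pairs a threshold with percentage rises, and hemoglobin adds a change criterion. No new data are needed. The cost is one extra table row, one count and one sign; the downside is small counts at about 30 patients per arm.

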1.4. Modifications from the Statistical Section in the Final Protocol

Only a single set of potentially clinically significant values (PCSV) tables will be provided for each applicable safety category (e.g., laboratory tests, electrocardiography, and vital signs). As the PCSV criteria defined in Section 14.3 are primarily defined in terms of changes from baseline, separate tables for patients in whom the PCSV criterion was normal or missing at baseline are not applicable.

Only listings required for the clinical study report will be produced.

In the definition of the on-treatment period for safety variables, mention of the date of patient last contact was removed; this text is not applicable as the date of patient last contact cannot be prior to the date of the last adverse event reported for an individual patient. In addition, the definition of the follow-up period for safety variables was modified to ensure a consistent reporting window for all patients.

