Hematocrit	>0.37 v/v at baseline and ≤0.37 v/v post-baseline for Male; ≥0.32 v/v at baseline and ≤0.32 v/v post-baseline for Female <0.55 v/v at baseline and ≥0.55 v/v post-baseline for Male; <0.5 v/v at baseline and ≥0.5 v/v post-baseline for Female	
Hemoglobin	>115 g/L at baseline and ≤115 g/L post-baseline for Male; >95 g/L at baseline and ≤95 g/L post-baseline for Female <185 g/L at baseline and ≥185 g/L post-baseline for Male; <165 g/L at baseline and ≥165 g/L post-baseline for Female Decrease from baseline by ≥20 g/L	Three criteria are independent. Criteria based upon decrease from baseline are more relevant than those based on absolute value. Other categories for decrease from baseline can be used (≥30 g/L, ≥40 g/L, ≥50 g/L).
Lymphocytes (ALC)	≤4.0 Giga/L at baseline and >4.0 Giga/L post-baseline	
Monocytes	≤0.7 Giga/L at baseline and >0.7 Giga/L post-baseline	
Neutrophils	≥1.5 Giga/L at baseline and <1.5 Giga/L post-baseline (Non-Black); ≥1.0 Giga/L at baseline and <1.0 Giga/L post-baseline (Black)	
Platelets	≥100 Giga/L at baseline and <100 Giga/L post-baseline <700 Giga/L at baseline and ≥700 Giga/L post-baseline	
RBC	≥4 Tera/L at baseline and <4 Tera/L post-baseline for Male; ≥3 Tera/L at baseline and <3 Tera/L post-baseline for Female <7 Tera/L at baseline and ≥7 Tera/L post-baseline for Male; <6 Tera/L at baseline and ≥6 Tera/L post-baseline for Female	Unless specifically required for particular drug development, the analysis is redundant with that of Hb. Otherwise, consider FDA criteria.
WBC	≥3.0 Giga/L at baseline and <3.0 Giga/L post-baseline (Non-Black); ≥2.0 Giga/L at baseline and <2.0 Giga/L post-baseline (Black) <16.0 Giga/L at baseline and ≥16.0 Giga/L post-baseline	

Parameter	PCSV	Comments
Urinalysis		
pH	>4.6 at baseline and \leq 4.6 post-baseline <8 at baseline and \geq 8 post-baseline	Two independent criteria
Vital Signs		
DBP	\leq 45 mmHg post-baseline and decrease from baseline by \geq 10 mmHg \geq 110 mmHg post-baseline and increase from baseline by \geq 10 mmHg	To be applied for all positions (including missing).
HR/Pulse Rate	\leq 50 beats per minute post-baseline and decrease from baseline by \geq 20 beats per minute \geq 120 beats per minute post-baseline and increase from baseline by \geq 20 beats per minute	
Respiratory rate	\geq 12 breaths per minute at baseline and $<$ 12 breaths per minute post-baseline \leq 20 breaths per minute at baseline and $>$ 20 breaths per minute post-baseline	

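### The female low-hematocrit PCSV rule in SAP 14.3 overlaps at exactly 0.32 v/v, so a woman unchanged at 0.32 is flagged

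*SAP*

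**What the plan says.** SAP 14.3 lists the PCSV criteria. Most rows pair a baseline condition with a post-baseline condition on the same cutoff, so that a patient counts only on crossing it. In the hematocrit row, the low-side rule for women is "≥0.32 v/v at baseline and ≤0.32 v/v post-baseline for Female".

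The neighbouring rules read:

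- low hematocrit, men: ">0.37 v/v at baseline and ≤0.37 v/v post-baseline for Male"
- high hematocrit, women: "<0.5 v/v at baseline and ≥0.5 v/v post-baseline for Female"
- low hemoglobin, women: ">95 g/L at baseline and ≤95 g/L post-baseline for Female"

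SAP 10.2 applies the criteria by "identifying patients with at least 1 post-baseline measurement that meets the PCSV criteria". It also states: "All measurements collected during the study, including values from unscheduled visits, will be used in the PCSV analyses".

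Protocol 11.4.5.2 had planned a second laboratory PCSV count, restricted to patients whose criterion was normal or missing at baseline. SAP 1.4 drops it, with this reason: "As the PCSV criteria defined in Section 14.3 are primarily defined in terms of changes from baseline".

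**The concern.** A crossing rule works only if no single value can satisfy both of its conditions. Here 0.32 satisfies both. A woman who enters at 0.32 and has one later reading of 0.32, scheduled or not, is counted as having a post-baseline PCSV with zero change.

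Because SAP 1.4 removes the separate tabulation by baseline status, the baseline clause inside each row is what separates a value already present at entry from one that arose on study. For women with low hematocrit, that separation breaks down at one value. At stake is the accuracy of one count in a descriptive safety table, and the fact that a programmer who follows the SAP literally will code the overlap.

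**Working it through.** The SAP states no figure to reproduce. The check is one of logic, followed by a rough size under stated assumptions.

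**Step 1. Does the cutoff satisfy both conditions?** Put the cutoff value itself into each side.

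| Rule in SAP 14.3 | Baseline condition at the cutoff | Post-baseline condition at the cutoff | Overlap |
|---|---|---|---|
| Hematocrit low, women (0.32) | 0.32 ≥ 0.32: true | 0.32 ≤ 0.32: true | yes |
| Hematocrit low, men (0.37) | 0.37 > 0.37: false | 0.37 ≤ 0.37: true | no |
| Hematocrit high, women (0.5) | 0.5 < 0.5: false | 0.5 ≥ 0.5: true | no |
| Hemoglobin low, women (95 g/L) | 95 > 95: false | 95 ≤ 95: true | no |

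The same test was applied to 44 single-threshold pairs from the table (chemistry, ECG, hematology, urine pH, respiratory rate). Only the female low-hematocrit pair overlaps. Rows with ≥ at baseline, such as chloride, potassium, neutrophils, platelets, RBC and WBC, use a strict < afterwards. The compound rules (glucose, eosinophils, transaminases with bilirubin) are exact complements.

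**Step 2. What does the rule flag near the boundary, and what would each repair flag?**

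| Baseline → later value | As written | >0.32 then ≤0.32 | ≥0.32 then <0.32 |
|---|---|---|---|
| 0.32 → 0.32 | flagged | not flagged | not flagged |
| 0.33 → 0.32 | flagged | flagged | not flagged |
| 0.32 → 0.31 | flagged | not flagged | flagged |
| 0.31 → 0.31 | not flagged | not flagged | not flagged |
| 0.33 → 0.33 | not flagged | not flagged | not flagged |

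Only 0.32 → 0.32 is wrong under both repairs. Whether 0.32 → 0.31 is a false flag depends on which form was intended.

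**Step 3. How many women could be at the boundary?** All inputs are assumptions, since the documents give none: hematocrit in women normal with mean 0.40 and SD 0.030 to 0.040, and about 30 women among the approximately 60 patients.

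- *Reported to 2 decimals.* P(0.315 ≤ X < 0.325) = 0.39% at SD 0.030, 0.85% at SD 0.035 and 1.36% at SD 0.040. Times 30 women: 30 × 0.0039 = 0.12 to 30 × 0.0136 = 0.41, or roughly 0.1 to 0.4.
- *Reported to 3 decimals.* P(0.3195 ≤ X < 0.3205) = 0.04% at SD 0.030 and 0.13% at SD 0.040. Times 30 women: 30 × 0.0004 = 0.012 to 30 × 0.0013 = 0.039, or roughly 0.01 to 0.04.

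These are expected numbers of women with a baseline at the boundary, both arms together. A wrong flag also needs a later value at the boundary, so fewer would be flagged.

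**The case against.** The strongest objection is that everything rests on one character. Text extracted from a PDF can turn > into ≥, and the text alone cannot rule that out. This stands as a reason to look at the printed page first. It does not dispose of the point, because the other signs in the same row read coherently and nothing else in the SAP overrides the rule.

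Second, the table does not use a single form. Neutrophils, platelets, RBC and WBC pair ≥ with <, so the faulty sign could be the post-baseline one, in which case 0.32 → 0.31 is correctly flagged. This also stands, and it limits the certain error to 0.32 → 0.32. The closest comparators, male hematocrit and both low-hemoglobin rules, use > then ≤, which makes the baseline sign the likelier slip.

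Third, a reader might infer that the baseline condition fails for the whole row, so that pre-existing low values in general would appear as new findings once the separate tables are dropped. The documents do not support that. Every woman below 0.32 at baseline is still excluded, and the failure is at one value. SAP 1.4 says only that the criteria are primarily change-based. The temperature row, for example, has no baseline condition at all.

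A reader might also note that one flag in an arm of about 30 is 1/30 = 3.3 percentage points and infer a distorted safety comparison. That figure is conditional on an event whose baseline precondition alone is expected in only about 0.01 to 0.4 women in the trial. In addition, SAP 10.2 summarizes laboratory values and their change from baseline. The hemoglobin row has its own thresholds and a criterion for a decrease of at least 20 g/L, so an isolated hematocrit flag could be checked against them.

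**Conclusion.** The rule is wrong as written, but narrowly. On the text of SAP 14.3, a woman at exactly 0.32 v/v both at baseline and later is counted as a PCSV with no change, and no other threshold-crossing pair in the table has this overlap. That conclusion needs no assumption beyond the sign being printed as ≥.

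The size is very small and rests wholly on the assumptions in the working. Reporting precision alone moves the estimate about tenfold. One descriptive safety count is affected. The primary endpoint, its test and every other efficacy result are untouched. It is an inconsistency in an inequality sign, worth correcting because the correction is trivial, and it is not evidence of a false safety signal.

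**What to change.** Check the sign on the source page of SAP 14.3 and in the PCSV program. If it is >, the point closes. If it is ≥, change the female low-hematocrit rule to >0.32 v/v at baseline and ≤0.32 v/v post-baseline, which has the same form as the male hematocrit rule and both low-hemoglobin rules. Align the program and document the correction.

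The alternative, ≥0.32 then <0.32, also removes the overlap but treats 0.33 → 0.32 and 0.32 → 0.31 the opposite way. The choice should therefore be made explicitly and not left to the programmer. The cost is one character in the SAP and one in the code.
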